## 13.7 Analysis of Secondary Endpoints

To address secondary objective 1.3.2.1, additional pharmacokinetic parameters, including clearance, Cmax, and terminal half-life, for uproleselan will be calculated using standard methods and reported descriptively, in aggregate and by assigned dose level.

To address secondary objective 1.3.2.2, Kaplan-Meier curves of leukemia-free survival (LFS), overall survival (OS), and non-relapse mortality (NRM) will be generated for the cohort treated at the RP2D, and the point estimates of 1-year LFS, OS, and NRM will be calculated, with standard error according to Greenwood.

To address secondary objective 1.3.2.3, the proportion (and corresponding 95% exact confidence interval [CI]) of patients who experience oral and/or gastrointestinal mucositis will be summarized by severity.

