# **OBJECTIVES**

#### 1.1 Hypothesis

The long range hypothesis of this project is that incorporating uproleselan into pre-transplant conditioning for acute myeloid leukemia will decrease post-transplant relapse and improve leukemia free survival.

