#### 1.4 Secondary Objectives

- 1) To describe the pharmacokinetics of uproleselan in pediatric patients receiving myeloablative, busulfan based pre-transplant conditioning (this will encompass both phase 1 and phase 2).
- 2) To describe the preliminary efficacy of uproleselan by estimating the 12-month leukemia-free survival (LFS), overall survival (OS), and relapse in patients receiving uproleselan at the RP2D
- 3) To describe the maximal severity of oral and gastrointestinal mucositis in patients receiving uproleselan at the RP2D.

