#### 3.1.5 **Disease status:**

Multidimensional flow cytometry (MDF) to assess disease status for eligibility will be performed centrally by Hematologics.

- In a first or second complete remission (defined as marrow with ≤1% leukemic blasts by MDF and no evidence of extramedullary disease) with minimal residual disease (MRD, defined as marrow with ≥0.05% leukemic blasts by MDF) after at least 2 cycles of induction/re-induction chemotherapy.
- Have newly diagnosed disease or disease in first relapse that is refractory (defined as marrow with >1% leukemic blasts by MDF or persistence of extramedullary disease) to at least 2 cycles of induction/re-induction chemotherapy.

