#### 13.2.2 Secondary Endpoints

Leukemia-free survival: The time from transplant to the first occurrence of an event (leukemic relapse [section 11.2] or death from any cause), or censored on date of last contact, if no event occurs.

Overall survival: The time from transplant to death from any cause, or censored on date of last contact, if no death occurs. **Cause of death will be classified according to CIBMTR consensus criteria**.

Non-relapse mortality: The time from transplant to death while in continuous complete remission, or censored on date of last contact, if no death occurs.

Relapse: The time to leukemic relapse.

Oral and gastrointestinal mucositis endpoint. The occurrence and severity of oral or gastrointestinal mucositis (between day 0 and post-transplant day 14) as graded by CTCAEv5.0.

Neutrophil engraftment: time to the first of 3 consecutive days following the nadir that the absolute neutrophil count is at least  $500/\mu$ l.

Platelet engraftment: time to the first day following the nadir that the platelet count is at least  $20,000/\mu$ l without a transfusion in the preceding 7 days.

Mucosal barrier injury-associated laboratory-confirmed bloodstream infection (MBI-LCBI) : cumulative incidence of MBI-LCBI by Day +30.

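### Section 13.7 plans non-relapse mortality where objective 1.4(2) names 12-month relapse, and the LFS and NRM definitions do not fit the refractory patients the trial enrols

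*Protocol*

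**What the plan says.** The hypothesis in section 1.1 is that uproleselan "will decrease post-transplant relapse and improve leukemia free survival". Secondary objective 2 in section 1.4 is to describe preliminary efficacy by "estimating the 12-month leukemia-free survival (LFS), overall survival (OS), and relapse in patients receiving uproleselan at the RP2D".

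Section 13.7 answers that objective (cited there under the number 1.3.2.2). On the curves it states: "Kaplan-Meier curves of leukemia-free survival (LFS), overall survival (OS), and non-relapse mortality (NRM) will be generated for the cohort treated at the RP2D". For the 12-month figures its wording is: "the point estimates of 1-year LFS, OS, and NRM will be calculated, with standard error according to Greenwood". No estimate of relapse is named.

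The definitions are in 13.2.2:

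- LFS: "The time from transplant to the first occurrence of an event (leukemic relapse [section 11.2] or death from any cause".
- NRM: "The time from transplant to death while in continuous complete remission, or censored on date of last contact, if no death occurs".
- Relapse: time to leukemic relapse, with no section cited.
- Under OS: "Cause of death will be classified according to CIBMTR consensus criteria".

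Section 3.1.5 admits two groups: patients in remission with residual disease, and patients who "Have newly diagnosed disease or disease in first relapse that is refractory". Section 11.1 defines persistent leukemia at the Day +30 evaluation. Section 11.2 (relapse) applies to patients in remission at transplant, or who reach remission by the Day +30 assessment, and its only subsection is bone marrow relapse. Extramedullary and CNS relapse are in 11.3. Section 13.8 uses LFS status at 1 year in both exploratory analyses.

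**The concern.** Relapse is what the hypothesis is about, and it is the one quantity in the objective for which 13.7 gives no estimate. NRM, which takes its place, appears in no objective.

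The definitions were written for patients who are in remission, but part of the cohort will not be. Two consequences follow. A living patient who never cleared leukemia counts as leukemia-free, an error that can only flatter the treatment and that passes into the E-selectin analyses. A refractory patient who dies of toxicity before remission is assessed is not in continuous complete remission, so that death is not NRM.

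Kaplan-Meier is also the wrong estimator for NRM when relapse is a competing event.

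**Working it through.** **1. Objective against analysis.**

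| Quantity | Objective 1.4(2) | Defined in 13.2.2 | Estimated in 13.7 |
|---|---|---|---|
| LFS | yes | yes | yes |
| OS | yes | yes | yes |
| Relapse | yes | yes | no |
| NRM | no | yes | yes |

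The study calendar and section 10.3.6 follow relapse to two years (Day +730), so the data will exist.

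**2. LFS and persistent leukemia.** Take a patient refractory at transplant who still meets section 11.1 at Day +30. Section 11.2 does not apply, because remission was not reached by the Day +30 assessment. The only LFS event left is death. If the patient is alive at 12 months, LFS is overstated by 1/20 = 5 points. The protocol gives neither the refractory share f, nor the share p of those with persistent disease, nor the share s of those alive at 12 months. The overstatement is f × p × s. Under two sets of assumed ranges:

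- f 30–70%, p 10–30%, s 10–30%: 0.3 × 0.1 × 0.1 = 0.3 points to 0.7 × 0.3 × 0.3 = 6.3 points.
- f 25–75%, p 20–40%, s 0–50%: 0 to 0.75 × 0.4 × 0.5 = 15 points.

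The spread comes from the assumptions. Only the 5 points per patient is firm.

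**3. LFS and extramedullary relapse.** LFS cites 11.2, while extramedullary and CNS relapse are in 11.3. Read literally, an isolated relapse of that kind is not an LFS event.

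**4. Kaplan-Meier for NRM.** The plan states no figure to reproduce. Assumed inputs: true 12-month NRM of 10% (section 2.3 reports 10.3% at 3 years on the same backbone); relapse R of 22.5% (the AML figure in section 2.3), 40% or 60%; constant hazards.

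*Censored at relapse:* H = −ln(1 − 0.10 − R), and 1−KM = 1 − exp(−H × 0.10/(0.10 + R)). At R = 60%, H = 1.204 and the NRM part is 0.172, so 1−KM = 15.8%.

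*Literal text:* censoring is stated only for patients who do not die, so relapsed patients stay at risk. The NRM hazard is then diluted to the NRM density divided by (relapse-free + alive after relapse). This was integrated numerically over 12 months for median post-relapse survival of 12, 6 and 3 months. The text does not say what happens at a death after relapse; here the patient leaves the risk set at that point.

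| Relapse | Literal: 12 / 6 / 3 months | Censored at relapse |
|---|---|---|
| 60% | 10.7 / 11.3 / 12.3% | 15.8% |
| 40% | 10.4 / 10.8 / 11.4% | 12.9% |
| 22.5% | 10.2 / 10.4 / 10.7% | 11.4% |

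Standard error at n=20: √(0.10 × 0.90/20) = 6.7 points.

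**5. NRM definition.** Remission after transplant is assessed at Day +30 ± 5 days. A refractory patient who dies of toxicity before then has no documented remission and is not an NRM event. Each such death lowers NRM by 1/20 = 5 points. It still counts in OS and LFS, and in TRM, which covers death from any cause through Day +100 (section 13.5).

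**The case against.** The strongest reply is that relapse is not lost. It is an objective, a defined endpoint with detailed criteria, and it is followed for two years; an estimator can be left to an analysis plan. That stands as far as it goes: a reader might infer that the trial cannot report relapse, and the documents do not support this. But 13.7 is not silent. It lists the quantities for this objective and puts NRM where the objective says relapse.

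Three other stronger readings also fail:

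- *Every patient who never remits inflates 12-month LFS.* Only those still alive at 12 months do, because death is an LFS event.
- *The plan means to exclude extramedullary relapse from LFS.* This is more likely a numbering slip: 11.2 carries the general title but holds only marrow relapse, and the separate relapse endpoint cites no section.
- *NRM will be badly overstated.* The 15.8% needs censoring at relapse, which the text does not state. On the literal text the excess is 0.2 to 2.3 points, small beside 6.7. The estimator pushes NRM up and the definition pushes it down, so the documents do not settle the direction of the combined error.

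It is also fair that all these outputs are secondary or exploratory and descriptive at n=20, and that no decision rests on them.

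**Conclusion.** The point holds and should be corrected. Two parts rest on comparing the text alone: 13.7 gives no relapse estimate for an objective that names one, and LFS has no event for a living patient with persistent leukemia at Day +30. The second matters most for the results, at 5 points of LFS per affected patient alive at 12 months, always in the favourable direction. The number affected cannot be derived from the protocol.

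The missing reference to 11.3 needs only a corrected cross-reference. The NRM estimator and definition are minor: 10.2–12.3% on the literal text, or 11.4–15.8% with censoring at relapse, against an assumed true 10%, under constant hazards and assumed relapse of 22.5–60%. DLT, OS and the TRM and RRT rules are unaffected.

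**What to change.** **Section 13.7.** Add the 12-month cumulative incidence of relapse (sections 11.2 and 11.3), with death without relapse and persistent leukemia as competing events. Estimate NRM by cumulative incidence (Aalen-Johansen, with a matching variance), with relapse and persistent leukemia or leukemia death competing. Keep Kaplan-Meier with Greenwood standard errors for LFS and OS.

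**Section 13.2.2.** Let LFS cite 11.1, 11.2 and 11.3, and count persistent leukemia at Day +30 as an event. The sponsor should state how a later remission is treated; the protocol does not compel either choice. Define NRM as death without prior relapse or documented persistent leukemia and not caused by leukemia, using the CIBMTR classification already specified. Toxic deaths of refractory patients before Day +30 then count as NRM.

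**Section 13.8.** Use the same LFS status.

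**Cost.** A few lines of text. The Day +30 evaluation and the cause-of-death classification are already planned, so no new data are needed. LFS will be slightly less favourable if some refractory patients do not remit. Sample size and monitoring rules stay as they are.

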Importantly, BFC has been extended to a large group of children and adolescents at the Leiden University Medical Center and University Medical Center Utrecht transplant centers in the Netherlands. 155 children (median age 9.7 years) with hematologic malignancies were enrolled, including 69 with AML (28 in CR1, 40 in CR2, 1 with active disease). 119 patients received transplants from unrelated donor. Most patient received either bone marrow (n=79) or cord blood (n=66) grafts. There were only 2 cases of non-engraftment. Non-relapse mortality at 3 years was 10.3%. No veno-occlusive disease of the liver was observed. The cumulative incidence of relapse in AML was 22.5% and event free survival for patients transplanted in AML in 1st CR and 2nd CR was 64% and 65%, respectively. These results demonstrate that in pediatric patients BFC is safe, well suited for cord blood transplantation and effective for AML.

BFC was chosen for use as the conditioning backbone in this trial because it may be more effective in patients with chemotherapy-resistant AML, because it is safe in pediatric patients and because it is immunosuppressive enough to produce robust engraftment in cord blood transplantation.

The current trial builds on other recent attempts to add novel chemotherapy agents to BF or BFC conditioning in adults with AML. The list of agents that have been tested or are currently being tested in early phase trials includes plerixafor, CPX-35121 and vorinostat (NCT02083250).

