# 2.4 Rationale

This phase 1/2 trial will allow us to prepare for a full-scale clinical trial, open to patients with chemo-sensitive as well as chemo-resistant AML and to patients receiving a wider variety of donor/graft types and forms of conditioning and GVHD prophylaxis. We anticipate that in the full-scale clinical trial, patients with chemo-sensitive disease will be assigned to a randomized stratum (uproleselan vs. placebo), while patients with chemo-resistant disease will be non-randomly assigned to treatment with uproleselan.

Eligibility: Eligibility for the trial will be limited to those patients at highest risk for relapse: those transplanted with refractory disease (not in remission) or transplanted in a complete remission, but with measurable residual disease on marrow testing by multidimensional flow cytometry (MRD positive). The risk of relapse associated with pre-transplant MRD approaches that associated with refractory disease. A large analysis of children and adults transplanted for AML in first or second complete remission (CR1 or CR2) showed that patients with any level of MRD pre-transplant had a nearly five-fold higher risk of relapse at 3 years compared to those who were MRD negative. Importantly, pre-transplant MRD obviated the significance of traditional risk factors, including cytogenetic risk and remission number. Similar results were shown in a pediatric only cohort in the Pediatric Blood and Marrow Transplant Consortium study ONC001 for patients receiving allo-HSCT in CR1 or CR2. The 2-year cumulative incidence of

relapse was 32% for the 113 patients who were MRD negative prior to HSCT as compared to 70% for the 10 patients who were MRD pos. (p=0.01). In both of these studies, most of the relapses in patients who had pre-HSCT MRD occurred by 6 months. In both studies, relapse-free survival for MRD positive patients was approximately 40% at 6 months.

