# **13. STATISTICAL CONSIDERATIONS**

This is a prospective, multicenter, single treatment arm phase 1/2 clinical trial. Phase 1 will proceed according to a standard 3+3 design. Phase 2 will expand enrollment to N=20 patients at the RP2D identified in Phase 1 to confirm safety and estimate preliminary efficacy. In phase 2, interim monitoring will be performed for transplant-related mortality within 100 days of transplant (see section 13.5).

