## 13.3 Sample Size, Accrual Rate and Study Duration

During Phase 1, a minimum of 3 evaluable patients will be required (if 0 out of 3 patients at dose level 1 experience a DLT, the RP2D has been identified). A maximum of 12 evaluable patients will be required (6 patients at dose level 1 followed by 6 patients at dose level 0).

During Phase 2, an additional 14 to 17 evaluable patients will be required to reach a total of 20 evaluable patients treated at the RP2D. A sample size of 20 evaluable patients achieves an exact 95% confidence interval width equal to 0.379 assuming that the observed proportion of patients experiencing a DLT is 0.20.

Total Sample Size. A minimum of 3 and a maximum of 26 evaluable patients will be required. To account for up to 2 potentially unevaluable patients, a maximum sample size of up to 28 patients is anticipated.

Study Duration. Assuming an accrual rate of 1 patient per month, accrual of the up to 28 patients will take about 2 years and 4 months, plus 2 years of follow-up on the last patient, for a total study duration of about 4 years 4 months.

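### One-year non-relapse mortality is given only a Greenwood standard error, which is zero when no non-relapse death occurs among the 20 patients (minor; NRM only)

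*Protocol*

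**What the plan says.** Section 13.7 plans Kaplan-Meier curves of LFS, OS and NRM for the cohort treated at the recommended phase 2 dose. It adds that "the point estimates of 1-year LFS, OS, and NRM will be calculated, with standard error according to Greenwood". No confidence interval is named for these three endpoints.

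The next paragraph of the same section treats mucositis differently and reports "the proportion (and corresponding 95% exact confidence interval [CI]) of patients who experience oral and/or gastrointestinal mucositis". Section 13.6 plans 95% intervals for toxicities. Section 13.3 supports the sample size with an exact interval: "A sample size of 20 evaluable patients achieves an exact 95% confidence interval width equal to 0.379".

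Other relevant places:
- Cohort size (section 13): "Phase 2 will expand enrollment to N=20 patients at the RP2D identified in Phase 1".
- NRM definition (section 13.2.2): "The time from transplant to death while in continuous complete remission, or censored on date of last contact, if no death occurs". It does not say how a relapse is handled.
- The NRM benchmark (section 2.3, used again in section 13.5): "Non-relapse mortality at 3 years was 10.3" per cent.
- Background on relapse (section 2.4): "relapse-free survival for MRD positive patients was approximately 40% at 6 months".

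**The concern.** Greenwood's formula sums over event times, so it returns 0 when there are no events, however few patients were observed. It also leads naturally to a symmetric interval, which is too short on the upper side when the estimate is near 0. NRM is the one endpoint in this sentence where the protocol's own benchmark makes 0, 1 or 2 events in 20 patients likely.

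Section 2.4 says that the trial is meant to prepare a full-scale trial. An NRM reported as 0% with a standard error of 0% would suggest a certainty that 20 patients cannot give, and the error lies in the unsafe direction. The 20-patient cohort gets an exact interval for mucositis but none for mortality without relapse.

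**Working it through.** **Inputs.** n = 20 (section 13). Benchmark NRM 10.3% at 3 years (section 2.3). A true rate of 5% is added as an assumption, to show the range. Assumption for the binomial figures: all 20 patients are followed to 1 year and stay in the risk set.

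**Check on the protocol's own figure.** The exact (Clopper-Pearson) 95% interval for 4 of 20 is 0.057 to 0.437, a width of 0.379. This reproduces section 13.3.

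**Formula.** With no censoring before 1 year, Greenwood reduces to SE = √(p(1−p)/n).
- 0 deaths: SE = 0
- 1 death: √(0.05 × 0.95/20) = 0.0487
- 2 deaths: √(0.10 × 0.90/20) = 0.0671
- 3 deaths: √(0.15 × 0.85/20) = 0.0798

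**NRM: three ways to express the uncertainty**

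| Deaths in 20 | Estimate ± 1.96 SE | Exact 95% | Log-log 95% | Upper limit, exact minus symmetric |
|---|---|---|---|---|
| 0 | 0 to 0 | 0 to 16.8% | undefined | 16.8 points |
| 1 | −4.6 to 14.6% | 0.1 to 24.9% | 0.7 to 30.5% | 10.3 points |
| 2 | −3.1 to 23.1% | 1.2 to 31.7% | 2.6 to 34.4% | 8.6 points |
| 3 | −0.6 to 30.6% | 3.2 to 37.9% | 5.1 to 39.6% | 7.2 points |

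The upper limit for 0 of 20 is 1 − 0.025^(1/20) = 0.168.

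**How likely these outcomes are.** The chance of no death is (1−p)^20.
- At 10.3%: 0.897^20 = 0.114. The chance of 0 to 2 deaths is 66%.
- At 5%: 0.95^20 = 0.358. The chance of 0 to 2 deaths is 92%.

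**Coverage of a nominal 95% interval, by exact enumeration.**
- ±1.96 SE: 88% at 10.3% and 64% at 5%. Almost all misses are upper limits below the true rate.
- Log-log, with the exact interval when there are no events: about 95% at 10.3% and 92% at 5%.

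**LFS and OS.** At an estimate of 40% the symmetric interval is 18.5 to 61.5% and the exact one 19.1 to 63.9% (widths 0.429 and 0.448). Symmetric coverage is 93 to 96% for event rates of 40 to 70%. At a 40% event rate the chance of no event is 0.6^20, about 0.00004.

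**If relapses are censored.** The risk set for NRM then shrinks, and the figures above for one or more deaths no longer apply. One death with 10 patients at risk gives an estimate of 10% with SE √(0.1 × 0.9/10) = 9.5%, in place of 5% and 4.9%. The estimate itself is also biased upward. Under assumed constant hazards with 1-year relapse R and true 1-year NRM N, 1 − KM = 1 − (1−R−N)^(N/(R+N)).
- R = 0.40, N = 0.10: 1 − 0.50^0.2 = 12.9%
- R = 0.60, N = 0.10: 1 − 0.30^(1/7) = 15.8%

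The zero standard error with no events holds on either reading.

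**The case against.** The strongest reply is that Greenwood is the standard variance for a Kaplan-Meier estimate and is also the input to a log-log interval. Section 13.7 does not prescribe estimate ± 1.96 SE, and the type of interval is commonly left to the statistical analysis plan. This stands. A reader might infer that the protocol has chosen a symmetric interval with 64 to 88% coverage, but it has not. Those figures describe what a reader would get from a bare standard error. The zero standard error does not depend on that use.

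A reader might also extend the criticism to all three endpoints. The documents do not support this. Patients are refractory or MRD-positive, section 2.4 reports high early relapse, and in the middle of the range the standard error performs well.

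A third tempting reading is that a safety conclusion rests on this standard error. It does not. The mortality decision in section 13.5 is a separate binomial rule on deaths to Day +100. Secondary objective 2 is descriptive ("To describe the preliminary efficacy of uproleselan by estimating the 12-month leukemia-free survival (LFS), overall survival (OS), and relapse") and does not list NRM.

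The contrast with mucositis partly reflects binary against time-to-event data, so it is not a contradiction. The 10.3% is also a 3-year figure from a cohort in which only 1 of 69 AML patients had active disease, so NRM here may differ. At a higher true rate, zero deaths would be less likely.

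**Conclusion.** The point holds as a minor reporting weakness limited to NRM. The measure of uncertainty that section 13.7 names is 0 when no non-relapse death occurs, although 0 of 20 is compatible with a rate up to 16.8%. The chance of this is about 11% at a true 1-year rate of 10.3%, and 36% if the rate were 5%. With 1 or 2 deaths, a reader who applies ±1.96 SE would put the upper limit 9 to 10 points too low compared with the exact limit.

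These figures assume complete follow-up of all 20 patients to 1 year, with relapsed patients kept in the risk set; section 13.2.2 does not settle the latter. If relapses are censored, the larger problem in the same sentence is Kaplan-Meier itself, which overstates NRM. LFS and OS are not materially affected.

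**What to change.** In section 13.7, replace the Greenwood clause with wording to this effect:

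- One-year LFS and OS are reported with two-sided 95% confidence intervals on the complementary log-log scale, using the Greenwood variance.
- One-year NRM is reported as a cumulative incidence with relapse as a competing event, with a log-log 95% confidence interval from the variance of that estimate.
- If no non-relapse death occurs, an exact binomial upper bound is given, based on the patients whose 1-year status is known, with the confidence level stated. The 16.8% above is the upper limit of the two-sided 95% interval for 20 such patients.

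The third item is needed because the log-log interval is undefined with no events. The restriction to patients with known status is needed because a binomial bound on all 20 would not be valid if some were lost before 1 year.

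The cost is a few lines of protocol or SAP text and no extra data. The only downside is a wider reported interval for NRM.
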